4.0 Schema

1. Patients may be offered enrollment in UNC Health Registry/Cancer Survivorship Cohort (CSC) if eligible and CSC is operational in their clinic or offered enrollment in LCCC1108 alone.
2. Normal specimen may be collected adjacent to tumor, blood sample, buccal swab etc. but this is not required.
3. See section 6.0 for definition of successful sequencing. The PFS will be documented in cancer patients with active disease (see section 1.4)

4.1 Study Methods and Procedures: Screening and Informed Consent

During the informed consent process, patients will be informed that results of some (but not all) of the genetic testing on their tumor specimens may be communicated directly to them through their treating physician. Along with the results that are communicated, the participant's treating physician will explain the implications of their testing results, including whether their genetic profile renders them eligible for a specific therapy or clinical trial, and/or if their genetic profile carries any prognostic significance for their disease. Participants will be informed that any specimens remaining after genetic profiling of their tumor to support their clinical care is complete, will be stored indefinitely and may be used for future unspecified research related to cancer. This may include development of cell lines or commercial products from their specimens.

We will inform patients that researchers may contact them in the future to request their participation in new research or in the event new discoveries or therapies become available that may be applicable to their specific genetic profile. We recognize that some patients may transfer their care to an outside institution. In the event a participant moves or transfers his or her care to an outside institution, he or she will be asked to contact the Study Coordinator to provide information about his or her disease status.

As is standard with all trials that may incorporate germ-line studies, we will inform patients of the potential implications for family members and the risks associated with such studies, including those related to insurability and employment and the limitations of laws designed to protect against such risks. However, it will be made clear to patients that although a blood sample is being obtained that may be used for comparison to their germline genome sequence, this study is not aimed at discovering germline mutations. We will emphasize that our analyses should not be construed as genetic testing for genetic mutations associated with hereditary cancer susceptibility. Nevertheless, because of the methods used, it is possible that we will discover a germline mutation that predisposes to cancer, in which case this information will be conveyed to the participants and their families through standard genetic counseling.

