PROTOCOL AMENDMENT # 9

LCCC 1108: Development of a Tumor Molecular Analysis Program and Its Use to Support Treatment Decisions

AMENDMENT INCORPORATES:

- X Editorial, administrative changes (IRB Approval)
- X Scientific changes (IRB approval)
 - Therapy changes (IRB approval)
 - Eligibility Changes (IRB approval)

AMENDMENT RATIONALE AND SUMMARY

In this amendment, some objectives have been appropriately reclassified as exploratory, and the plans for analysis have been amended to reflect the developing understanding of the study.

This amendment includes the following changes:

Editorial and Administrative Changes

- The study statistician has changed from [name] to [name].
- Per current practice, names of co-investigators are no longer listed.

Scientific Changes

- Section 2: Secondary objectives have been re-categorized as exploratory objectives due to this set of objectives being less informative than originally anticipated. Wording has also been clarified in Section 2.2.1.
- Section 6.1 and 6.2: Edits were made to reflect the planned analyses. These changes include deleting obsolete language from the Sample Size and Accrual language in Section 6.1, and modifying the Data Analysis language in Section 6.2 to state the Kaplan-Meier method will be used.

The attached version dated July 25, 2019 incorporates the above revisions

ATTACH TO THE FRONT OF EVERY COPY OF THIS PROTOCOL

PROTOCOL AMENDMENT # 8

LCCC 1108: Development of a Tumor Molecular Analyses Program and Its Use to Support Treatment Decisions

AMENDMENT INCORPORATES:

- X Editorial, administrative changes
- X Scientific changes (IRB approval)
 - Therapy changes (IRB approval)
- X Eligibility Changes (IRB approval)
 - Other

AMENDMENT RATIONALE AND SUMMARY

The amendment includes the following changes:

1. This protocol now serves as a stand-alone study in all clinics even where the Health Registry is established.
 - a) The protocol still includes references to the health registry but involvement in the Health Registry is no longer required as was previously noted in the eligibility criteria. The schema in Section 4 was revised to reflect this change
2. The protocol now indicates that researchers may or may not collect normal tissue samples and they may analyze only tumor samples.
3. The protocol allows for the possible conduct of systematic germline DNA studies although this type of analysis is not required.

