It is expected that most LCCC1108 participants will provide samples through procedures that are part of their standard clinical care, and thus, the additional risk of providing tissue to be used in this research will be minimal. Many participants will already have tissue and/or blood specimens banked in TPF under the general TPF protocol (LCCC9001) or under another approved tissue banking protocol. Others, who are consented to LCCC1108 pre-operatively, will allow any surplus tissue and/or blood (after the standard diagnostic procedures have been completed) to be accessed, stored, and processed for the research described herein. Parental consent is required for all patients <18 years old. Separate consent documents are also required for minor children (7-14 years old) and adolescents (15-17 years old). Any participant <18 years of age must have tissue already banked, or be undergoing a procedure as part of their standard clinical care.

A subset of patients ≥ 18 years of age will be asked to submit tissue and blood specimens obtained from procedures without a specific identified clinical or diagnostic need, based on current clinical standards of care. Biopsies of vital organs (e.g., lung, liver etc.) will be restricted to those participants ≥ 18 years of age whose treatment offers no expectation of cure, such as patients with refractory solid tumors who relapse with metastatic disease, e.g. Other biopsies performed outside of clinical standard of care will be limited to those tumors that can be accessed without subjecting the participant to unreasonable risk, as determined by the physician performing the procedure.

Specimens will be analyzed for alterations in a panel of specific genes of cancer relevance, but only genetic variants of potential clinical interest will be released to the treating physician to disclose to the patient. Germline changes that are discovered by systematic analysis and deemed clinically relevant will be reported in the context of formal genetic counseling. Results of genetic tests from the “gene list” will be analytically validated in a CLIA-certified laboratory prior to distribution to the treating physician (see possible exception to this requirement noted below). Note: when results between NextGen sequencing and CLIA are discordant, results from the CLIA-certified laboratory only will be distributed to the treating physician.

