1.4.3 Characterization of Population and Treatment Outcomes

While several attempts have been made to document the proportion of specific genetic alterations in selected Phase I populations, the intervention in LCCC1108 will provide the opportunity to characterize the proportion of most of the known clinically relevant genetic alterations across a wide variety of tumors. [17-19] Specifically, as a primary objective, we will estimate the proportion of enrolled patients who have undergone successful sequencing and who have a reportable genetic variant identified via UNCseq™. The study intervention, includes the use of highly and ever evolving sequencing methods and genomic technologies that may be applied to both somatic and germline tissues, and correlated with extensive clinical annotation and outcome data. These technologies may associate known molecular alterations in a variety of tumors with prognosis and/or clinical outcomes. A primary objective of this study is to compare PFS ratios between cancer patients with active disease with a reportable genetic variant and those without a reportable genetic variant. We chose the PFS ratio as it is the approach already used and published by Von Hoff, and it allows the patient to serve as his or her own control. Whether disease is defined as active or not takes place at the time of the MTB meeting. In this context, a patient is considered to have active disease provided they have not been declared to have NED (no evidence of disease) and they are not in hospice. The PFS ratio is defined as the PFS after the first treatment post UNCseq™ results divided by the PFS post the most recent therapy prior to UNCseq™ on which the patient has just experienced progression. See section 4.4 for additional details on this endpoint.

Using clinical data from patients enrolled in this protocol, either through LCCC0906 (the CSC) or LCCC1108, we plan to facilitate explorations of any correlation between these genetic alterations and response to molecularly based treatment under this and future IRB-approved protocols. As a secondary

objective, we will compare PFS ratios between patients with active disease and a reportable genetic variant who were treated based on this variant versus those not treated based on this variant (see section 4.4).

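### The protocol is inconsistent on whether germline findings are incidental or systematically sought, and Section 4.1 does not have patients told that germline DNA may be analysed systematically.

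*Combined protocol and SAP*

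**What the plan says.** Section 4.1 describes what patients hear during consent. It opens with disclosure: "As is standard with all trials that may incorporate germ-line studies, we will inform patients of the potential implications for family members", together with risks to insurability and employment and the limits of legal protection. It then qualifies this. Patients are told that "this study is not aimed at discovering germline mutations". The next sentence reads: "We will emphasize that our analyses should not be construed as genetic testing for genetic mutations associated with hereditary cancer susceptibility". The paragraph ends by conceding that "it is possible that we will discover a germline mutation that predisposes to cancer", attributes this to the methods, and says such a finding would be conveyed through genetic counselling.

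Sections 1.2.3 and 1.2.4 lean the same way. The first says comprehensive germline screening is not the purpose of the study, although it expects some inherited predispositions to come to light. The second says the study concentrates on somatic profiling of tumour.

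Section 1.4 takes a different position: "Germline changes that are discovered by systematic analysis and deemed clinically relevant will be reported in the context of formal genetic counseling". Section 1.4.3 describes the intervention as including "genomic technologies that may be applied to both somatic and germline tissues". Sections 4.1.3.1 to 4.1.3.3 allow germline DNA from blood, cheek swabs or other normal specimens to be released for molecular analysis.

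**The concern.** A finding that is stumbled on and a finding that is looked for are different things to a person deciding whether to take part. The chance of receiving a hereditary result depends on which applies, and so does the weight a participant or parent might give to the family, insurance and employment consequences that Section 4.1 lists. If germline DNA is analysed systematically and clinically relevant results are returned, a discussion that presents such results as an unsought by-product leaves out a material fact.

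The protocol's own background makes the distinction matter. Section 1.2.3 describes testing for high-penetrance germline mutations as including counselling and education before the test as well as when results are delivered. Section 4.1 describes genetic counselling only as the route for conveying a finding once made. That fits an unsought finding better than one produced by a deliberate search.

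**Working it through.** No arithmetic applies. The check is whether the current passages can all be true of the same participant.

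**Step 1: is the conflict in current text?** Yes. Every passage compared below stands in the body of the current protocol. The Amendment 8 summary is used only as context. It says "The protocol allows for the possible conduct of systematic germline DNA studies although this type of analysis is not required", which suggests that the wording in Section 1.4 was intended. The point does not depend on it.

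**Step 2: the passages side by side.**

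| Question | Sections 4.1, 1.2.3, 1.2.4 | Sections 1.4, 1.4.3 |
|---|---|---|
| Is germline discovery an aim? | No (4.1). Comprehensive screening is not the purpose (1.2.3). Germline profiling is not the focus (1.2.4). | Not stated as an aim. |
| How would a germline change be found? | Possibly, as a by-product of the methods (4.1). | By systematic analysis (1.4). |
| What is the normal specimen for? | Blood may serve for comparison (4.1). | The technologies may be applied to germline tissue (1.4.3). |
| What are the analyses? | Not to be taken as hereditary-susceptibility testing (4.1). | Analyses from which clinically relevant germline changes are returned (1.4). |
| How are results returned? | Through genetic counselling (4.1). | Through genetic counselling (1.4). |

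**Step 3: which rows conflict?** The first does not have to. A study can permit an analysis that is not among its aims, and no objective in Section 2 concerns germline discovery. The last row agrees. The second row conflicts, because an unsought by-product and the product of a systematic analysis are different accounts of how the same finding arises. In the third row, comparison with tumour is the only use of the blood sample that Section 4.1 mentions, while 1.4.3 leaves room for more. The fourth row is the most awkward. The sentence in 4.1 is about the analyses, not the aims, so the absence of a germline objective does not rescue it. Where germline DNA has been analysed systematically and a predisposing change returned, that assurance fits poorly with what was done.

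**Step 4: does Section 4.1 fill the gap elsewhere?** In part. It discloses possible germline studies, their risks and the return of findings. It never says that germline DNA may be analysed systematically. Section 4.1.2 and the privacy text in Section 4.3 repeat the counselling route, and the latter repeats the family and insurance risks. Neither supplies the missing statement.

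**Step 5: who is affected, and does it reach the estimates?** The inconsistency bears on participants whose germline DNA is systematically analysed. It does not bear on those whose normal specimen serves only for comparison with tumour, or on those with no normal specimen, since collection is optional. The wording of the consent discussion does not enter the definition of successful sequencing in Section 6.2, the exact confidence interval for the proportion, or the Kaplan-Meier estimate of 2-year PFS. The precision table in Section 6.1 depends only on the number successfully sequenced.

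**The case against.** The best defence is that Section 4.1 can be read as true and reasonably full. Saying that germline discovery is not the aim does not say that germline analysis will not be done. Section 2 has no germline objective, Section 6 contains no germline analysis, and Sections 1.2.3 and 1.2.4 describe purpose and focus consistently with 4.1. Patients are told that germline studies may be part of the trial, what the risks are, and that a predisposing mutation could be found and conveyed. On the other side, the sentence in Section 1.4 governs how changes are reported. It neither defines systematic analysis nor says that it will be run, and 1.4.3 is only permissive.

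Much of this stands, and it rules out stronger readings. A reader might infer that participants consent to a different study from the one permitted, or that they were told germline analysis was not being done. The documents support neither. Section 4.1 contains no such denial, systematic germline analysis is optional, and the consent pages are not among the documents available, so what participants and parents actually read cannot be checked. For the same reason nothing can be said about the consent basis for using germline data. A reader might also take the anticipated enrolment of up to 5000 as the size of the problem. That is total enrolment and does not count those affected.

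The defence does not remove the narrower inconsistency. Permission that is optional is still permission, and the consent discussion does not mention it. The disclosure of risks is followed directly by an assurance that points the other way, and the assurance that "our analyses should not be construed as genetic testing for genetic mutations associated with hereditary cancer susceptibility" is not answered by an argument about aims.

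**Conclusion.** The concern holds as an inconsistency in the protocol's account of germline findings, together with an omission in Section 4.1. It is a matter of participant protection, not of inference: no estimate, interval or sample-size figure changes. Its reach cannot be quantified, because the documents do not say how many participants have germline DNA analysed systematically, or whether any do.

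The conclusion rests on two assumptions. The first is that the reference in Section 1.4 to systematic analysis means what it says and is not leftover wording. The second is that the consent and assent forms follow the description in Section 4.1. If the forms already state that systematic germline analysis may be done, the defect is confined to the protocol text.

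**What to change.** Reconcile Sections 1.2.3, 1.2.4, 1.4, 1.4.3 and 4.1 so that the consent discussion matches the germline analysis actually permitted. The sponsor must decide which of two positions is intended:

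- Germline data serve only for comparison with tumour. Section 1.4 then loses its reference to systematic analysis, and 1.4.3 is limited accordingly.
- Systematic germline analysis is permitted. Section 4.1 then says that it may be done and that clinically relevant results may be returned, the assurance about hereditary-susceptibility testing is brought into line, and Sections 1.2.3 and 1.2.4 are adjusted to match.

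Changing Section 4.1 alone would leave Sections 1.2.3 and 1.2.4 with the old framing. Once the protocol agrees with itself, check the adult consent form, the parental consent and the separate forms for children and adolescents against it.

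The cost is protocol and, if needed, consent wording through the IRB. The statistical sections need no change.

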4.1.1 Requested Studies

Researchers at UNC's High Throughput Sequencing Facility (or other UNC research facility) will perform molecular studies on genes of relevance to cancer. DNA and/or RNA isolation will be performed under the direction of [name]. Genomic data analysis will be conducted under the direction of Dr. [name]. Based on these results, additional molecular studies may be performed, if appropriate. Only variants of clinical interest, as determined by the UNC CCGR, will be conveyed to the treating physician (see Appendix A). If possible, results of reportable genetic tests will be validated (whether confirmed or refuted) analytically in a CLIA-certified Laboratory prior to distribution to the treating physician. NOTE: See Section 1.2.5 for possible exceptions to the CLIA requirement.

Quality Control (QC) of Tissue Samples

Prior to molecular analysis of samples accessed under this protocol, it is essential that QC be performed by qualified personnel to ensure that the case diagnosis and tissue histopathology are adequately represented to permit successful DNA and RNA sequencing. A qualified person will perform this QC prior to molecular analysis.

4.1.2 Patient Communication

Results will be placed in the patient's medical record if confirmed by a CLIA-certified laboratory and signed off by the MTB. Notification of results of reportable genetic profiling will be provided to the patient's treating physician who will be responsible for sharing results with their patient. Negative reports (i.e. no alteration found) will also be reported. If a germline mutation is discovered that has clinical implications with respect to hereditary cancer predisposition, for example, this information will be conveyed through formal genetic counseling. Along with the results, the participant's physician will explain the implications of the testing, including whether their genetic profile renders them eligible for a specific therapy or clinical trial, and/or if their genetic profile carries any prognostic significance for their disease. Participants will be informed that researchers may contact them in the future, to request their participation in new research or in the event new discoveries or therapies become available that may be applicable to their specific genetic profile.

4.1.3 Normal Specimen Samples

NOTE: If the patient is co-enrolled in LCCC0906 (the CSC), LCCC0824 (IRB#09-0768), LCCC0121 (IRB#01-1283), and/or other specimen protocols that include collection and storage of normal specimens in the TPF, these samples may be accessed if sufficient quantities are available, if samples are of the appropriate type, and if distribution is approved by the PI of the study. The following sections apply to patients who are not co-enrolled into one of these protocols.

4.1.3.1 Blood Samples

During screening, potential study subjects should be queried about any medications they are taking (see Eligibility Criteria). If applicable, a pregnancy test (blood or urine) should be done. For patients undergoing biopsy, the physician performing the procedure will ensure the patient meets all institutional standards for the procedure, and may collect ~8mLs in a single yellow top ACD tube (i.e., collection of normal tissue is not required). Alternatively, the participant can have a blood sample obtained during pre-operative care or in the outpatient phlebotomy clinic as appropriate. Inpatient participants may have blood samples taken as part of their regular phlebotomy draw.

For eligible patients who are not undergoing biopsy, a single yellow top ACD tube may be collected (~8 mLs of blood) for storage within 28 days of consent (if

possible), unless the investigator deems another source of normal DNA (or RNA) is more appropriate (see below).

For storage, serum will be processed by and stored in TPF, with each aliquot assigned a unique identification code, as per standard TPF procedures. Genomic DNA (or RNA) may be obtained and appropriate germline DNA (or RNA) may be released to the High Throughput Sequencing Facility or other UNC research facility for molecular analysis.

4.1.3.2 Buccal (Cheek) Swab Collection

For patients in which blood sample collection is not obtained, we may obtain two buccal swabs from the inner cheek to obtain germline DNA. DNA will be isolated from the swabs, frozen, stored in the TPF, and given a unique identification code, as per standard TPF procedures. Genomic DNA may be obtained and germline DNA may be released to the High Throughput Sequencing Facility or other UNC research facility for molecular analysis.

